According to the previous study results, the decision in clinical practice to use Pradaxa® or established vitamin K antagonists (VKAs) depends on many factors related to: (a) The patient: health status, comorbid and demographic conditions, perception of anticoagulant treatment, understanding of the burden of the disease, access to the medication, educational measures informing about medications, and reimbursement status. (b) The treating physician: stroke risk assessment, bleeding risk assessment, adherence to guidelines, access and use of medical education, and overall local health care system. These factors in the real-world clinical practice vary in countries with different health care systems; patients who newly start anticoagulation treatment versus those have had anticoagulation experience already; and the initiation versus the mid-term follow-up on Pradaxa®. According to National Health Insurance (NHI) in Taiwan, Pradaxa® is prescribed to a newly diagnosed NVAF patient with stroke or systemic embolism, left ventricular ejection fraction < 40%, symptomatic heart failure (New York Heart Association Class ≥ 2), age ≥ 75 years, or age ≥ 65 years with one of the following risk factors: diabetes mellitus, coronary artery disease (CAD), or hypertension. Pradaxa® should not be considered if the patient has valvular heart disease, stroke within 14 days, serious stroke within 6 months, the risk of increasing ischemia, creatinine clearance (CrCl) < 30 mL/min, active liver disease, or pregnant.

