9.2.3 Study visits

Collection of patient data should be managed during routine practice visits. The time schedule below can only be a recommendation; if a patient does not visit the site at these time points, no visit will be conducted solely for study purposes. Visits must be performed face-to-face and cannot be performed by phone, email, or fax, as the patient has to complete the self-administered questionnaires (PACT-Q). The planned collection time points are as follows:

1. Baseline (e.g., the enrolment date for Cohort A; the date of initiation on Pradaxa® or VKA for Cohort B)
2. 30 to 45 days after baseline (initiation period)
3. 150 to 210 days after baseline (continuation period)

Data will be collected and recorded on the CRF at baseline and follow-up visits according to **Table 1**, if available.

Remark: This is a non-interventional, observational study, all the tests collected at baseline and subsequent visits will be performed as judged appropriate by the treating physicians, and the results of interest will be recorded only if they are available. This study does not require additional tests or examinations to be performed throughout the entire study period.

Baseline visit (Visit 1):

No data collection for study purposes must be performed unless the patient has consented to participate in the study. Once the patient has signed the informed consent form, the patient is considered to be enrolled in the study and patient details should be recorded on the enrolment log.

The following procedures will be performed at the baseline visit, and data will be collected from the medical chart and recorded on the CRF, **if available**:

- Sign informed consent form.
- Review of inclusion and exclusion criteria, and record date of inclusion.
- Collection of reimbursement status (reimbursed, partially reimbursed, or private pay).
- Collection of demographic data: age, gender, race, education level, height, weight[&], and BMI.
[&]Weight will be used to calculate BMI and creatinine clearance (CrCl).
- Collection of concomitant diseases/comorbidities in the medical history and at baseline.

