- Collection of concomitant diseases/comorbidities,⁸ risk factors,^{9,10} and medical history related to NVAF prior to enrolment, including diabetes mellitus, hypertension, ischaemic heart disease, congestive heart failure, left ventricular dysfunction, stroke, transient ischaemic attack, thromboembolism, vascular disease (myocardial infarction, peripheral artery disease, and complex aortic plaque), abnormal renal function,

abnormal liver function (e.g. cirrhosis), bleeding (e.g. prior major bleeding, predisposition to bleeding/anemia), and alcohol usage. These data will be used to calculate CHA₂DS₂-VASC score and HAS-BLED score[#].

- Collection of current concomitant therapies within 1 month prior to enrolment. Detail information (e.g. indication, start/stop date or ongoing, dosage, route, unit, and frequency etc.) will be recorded if available.
 - For the concomitant therapy as an element for CHA₂DS₂-VASC score or HAS-BLED score calculation^{9,10} including chronic dialysis or renal transplant due to abnormal renal function and medication usage predisposing to bleeding (antiplatelet agents or nonsteroidal anti-inflammatory drugs (NSAIDs)), information prior to enrolment will only be collected as **active/past or never occurred**.
- Collection of serum creatinine, if available, to calculate creatinine clearance (CrCl). The most updated data of serum creatinine assessed prior to enrolment will be collected. CrCl will be calculated according to Cockcroft-Gault formula (using weight collected at the baseline visit and the most updated serum creatinine assessed prior to enrolment).
- Collect the most updated data of lab assessment assessed prior to enrolment for CHA₂DS₂-VASC score and HAS-BLED score calculation^{9,10}. The lab assessments include renal function test (CrCl, as described above), liver function tests (bilirubin, aspartate aminotransferase (AST), alanine aminotransferase (ALT), and alkaline phosphatase (AP)), and international normalized ratio (INR), including prothrombin time (PT).
- For Cohort A only: Collect duration of previous treatment with VKA.
- For Cohort A only: Collect reasons for switching from VKA to Pradaxa[®].
- Document the dosing of Pradaxa[®].
- Patients will be asked to complete the following patient related questionnaires:
 - PACT-Q1 (Cohort B only)
 - PACT-Q2 (Cohort A only)

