9.3.5 Description and justification of patient questionnaires (PACT-Q[®])

The Perception of Anticoagulant Treatment Questionnaire (PACT-Q) was developed as a means to investigate patients' satisfaction with anticoagulant treatment and treatment

convenience in patients with deep venous thrombosis (DVT), pulmonary embolism (PE), or atrial fibrillation (AF).^{13,14} The PACT-Q is a self-administered questionnaire. It can be completed in about 10 minutes. No specific training is required to complete this document.

The original PACT-Q consists of 2 parts and contains 27 items:

1. The PACT-Q1 is composed of a single dimension (7 items), covering the expectations of patients regarding their anticoagulant treatment, and is to be administered before treatment initiation. Only patients in Cohort B (newly initiator) will receive the PACT-Q1 questionnaire at baseline.
2. The PACT-Q2 is composed of 3 dimensions covering: convenience (11 items), burden of disease and treatment (2 items), and anticoagulant treatment satisfaction (7 items). The PACT-Q2 is to be administered to patients once treatment is ongoing. The patients in Cohort A (switchers) will receive PACT-Q2 at all the 3 visits, while the ones in Cohort B (initiators) will receive the questionnaire at Visit 2 and Visit 3.

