9.7.1 Main analysis

Baseline demographic and clinical characteristics

Descriptive summary will be presented for baseline demographic and clinical characteristics of all patients enrolled in Cohort A, Cohort B Pradaxa® initiators, and Cohort B VKA initiators, respectively. For continuous variables, number of patients, mean, standard deviation (SD), median, Q1 (lower quartile), Q3 (upper quartile), minimum, and maximum will be presented. For categorical variables, frequency and percentage will be presented for each category.

Primary outcomes

For Cohort A, descriptive summary will be presented for PACT-Q2 score at baseline visit (Visit 1), Visit 2, and Visit 3 using measure of central tendency and variation (mean \pm SD, or median with inter-quartile range (IQR)). The PACT-Q2 score at Visit 2 and Visit 3 will be compared with the PACT-Q2 score at baseline visit, respectively, using paired t-test or Wilcoxon signed-rank test based on the distribution of the data.

For Cohort B, the patients newly initiated Pradaxa® or VKA will be matched with a ratio of 1:1 based on the propensity score. The covariates age, gender, body weight, CHA₂DS₂-VASC score, HAS-BLED score, kidney function (creatinine clearance), stroke and/or bleeding related risk factors, co-morbidities, and/or concomitant therapies, **if available**, will be included in the propensity score model. Details of the propensity score model and the matching procedure, such as the choice of algorithm and caliper width will be specified in the SAP. Descriptive summary of the baseline characteristics will be presented for and compared between the matched patients to check the balance of baseline characteristics between the two groups of Cohort B after propensity score matching. Moreover, standardized difference will be calculated as a measure of the balance of baseline characteristics after propensity score matching. Analyses of PACT-Q2 score will be performed on propensity score matched Pradaxa® initiators and VKA initiators. Descriptive summary will be presented for PACT-Q2 score at Visit 2 and Visit 3 using mean \pm SD, or median with IQR. PACT-Q2 score will be compared between matched Pradaxa® initiators and VKA initiators using paired t-test or Wilcoxon signed-rank test.

Secondary outcomes

For Cohort A, the PACT-Q2 score at Visit 2 and Visit 3 will be compared using paired t-test or Wilcoxon signed-rank test based on the distribution of the data.

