9.9 LIMITATIONS OF THE RESEARCH METHODS

A non-interventional study is the most suitable design for obtaining information about the use of medicines in everyday therapeutic practice and thus for clarifying questions in everyday therapeutic practice. However, observational methodology inherits the limitation of selection bias and generalizability. In addition, the observational design intends to collect available data that are recorded on medical charts. The lack of data of interest may be one of the limitations.

A number of different types of bias that could influence the data collection and analysis from these cohorts are summarized below. Consecutive enrolment will be employed to minimize selection bias. The entry criteria are non-restrictive and will permit the enrolment of a broad patient population. The choice of treatment is at the discretion of the investigator. Missing data will be handled as appropriate (see Section 9.7.4) to lower the effect of missing values. All efforts will be made to minimize loss to follow-up in patients who are enrolled. Adjustment for covariates and propensity score matching (PSM) will be used to correct for identified confounders and channeling bias which could occur due to preferential prescribing in relation to different risks for events of interest (e.g. if Pradaxa® is prescribed more frequently to high risk patients than to other treatments, a high rate of outcome events could be expected in the Pradaxa® group). Patient reported outcomes will be assessed using validated questionnaires within a limited period of time to minimize recall bias which refers to the phenomenon when the outcomes of treatment (either good or bad) may colour the patient's recollection of events prior to or during the treatment.

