## 8.4 Covariates and Subgroups

Demographic and clinical characteristics, including age, gender, BMI classification (BMI<18.5, 18.5≤BMI<24, 24≤BMI<27, BMI≥27), CHA2DS2-VASc score, HAS-BLED score, kidney function (creatinine clearance), stroke and/or bleeding related risk factors, will be

considered as covariates/predictors for conducting propensity score matching the two subgroups in cohort B.

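### Cohort B matching omits reimbursement status and baseline treatment expectations (PACT-Q1), so the Pradaxa versus VKA difference in PACT-Q2 may be confounded by either

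*SAP*

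**What the plan says.** Protocol section 7 states that "the decision in clinical practice to use Pradaxa® or established vitamin K antagonists (VKAs) depends on many factors". Its list of patient factors includes "perception of anticoagulant treatment, understanding of the burden of the disease, access to the medication, educational measures informing about medications, and reimbursement status".

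Two baseline items bear on that list. Protocol 9.2.3 has, at Visit 1, "Collection of reimbursement status (reimbursed, partially reimbursed, or private pay" as the three levels. The same visit includes PACT-Q1 for Cohort B only. Protocol 9.3.5 describes PACT-Q1 as "covering the expectations of patients regarding their anticoagulant treatment, and is to be administered before treatment initiation". Cohort B first completes PACT-Q2 at Visit 2.

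The propensity covariates in SAP 8.4 are age, gender, BMI class, CHA2DS2-VASc, HAS-BLED, creatinine clearance, and stroke or bleeding risk factors, all to be "considered as covariates/predictors for conducting propensity score matching the two subgroups in cohort B". Protocol 9.7.1 has body weight in place of BMI class and ends with "stroke and/or bleeding related risk factors, co-morbidities, and/or concomitant therapies". Neither list contains reimbursement status or PACT-Q1.

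Under SAP 11.2 and 11.3, matched pairs are compared by paired t-test or Wilcoxon signed-rank test, with no covariate in the outcome comparison. PACT-Q1 is a descriptive secondary endpoint. Protocol 9.9 says covariate adjustment and "propensity score matching (PSM) will be used to correct for identified confounders and channeling bias".

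**The concern.** Change from baseline is not available in Cohort B, so nothing except the matching protects the primary contrast from differences that existed before treatment. The matching variables suit a clinical-event outcome: they balance stroke risk, bleeding risk and renal function. The outcome is a patient questionnaire, and the only patient-reported baseline measure in this cohort is left out, as is a payment variable that the protocol itself counts among the drivers of choice.

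A patient who expects more of a treatment, or who pays for it, may be more likely to receive one drug and may also rate it differently. The Visit 2 and Visit 3 differences would then mix that prior position with experience of the drug, which is what Objective 1 is about. SAP 11.6 draws its conclusion from p < 0.05, so such a shift could be reported as a difference between treatments.

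**Working it through.** **1. Is either variable used?** The documents, side by side:

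| | Reimbursement status | PACT-Q1 |
|---|---|---|
| Driver of choice (Protocol 7) | named | perception is named; PACT-Q1 is the nearest measure |
| Collected at baseline (Protocol 9.2.3, Table 1) | yes | yes, Cohort B |
| Covariate list, Protocol 9.3.3 | no | no |
| Propensity model, Protocol 9.7.1 | no | no |
| Propensity model, SAP 8.4 | no | no |
| Outcome comparison, SAP 11.3 | no | no |
| Listed as collected at baseline, SAP 9.3 | yes | yes |
| In the SAP 9.3 sentence on what is summarized | no | yes |

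**2. Size.** The plan gives no effect size, SD or power, so there is no figure of its own to reproduce. What follows is an illustration.

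Inputs from the documents: about 500 Pradaxa and 200 VKA patients (SAP 7.4), so at most 200 pairs under 1:1 matching; two-sided 0.05 (Protocol 9.7).

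Assumed inputs: r, the correlation of PACT-Q1 with PACT-Q2, 0.1 to 0.5; d, the standardized PACT-Q1 difference left after matching, 0.1 to 0.5; within-pair correlation 0; no true drug difference.

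- Bias in SD units = r × d.
- SE = √(2/n). For n = 200, √0.01 = 0.100; for n = 150, 0.115.
- Rejection = P(Z > 1.96 − bias/SE) + P(Z < −1.96 − bias/SE).

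| r | d | Bias (SD) | Rejection, 200 pairs | Rejection, 150 pairs |
|---|---|---|---|---|
| 0.1 | 0.1 | 0.01 | 5.1% | 5.1% |
| 0.3 | 0.3 | 0.09 | 14.7% | 12.2% |
| 0.3 | 0.5 | 0.15 | 32.3% | 25.5% |
| 0.5 | 0.5 | 0.25 | 70.5% | 58.1% |

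For the second row at 200 pairs: 0.09/0.100 = 0.9, and P(Z > 1.06) + P(Z < −2.86) = 0.145 + 0.002 = 0.147.

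**3. Does using the variable remove the bias?** A simulation of 700 patients (400 runs per setting, no drug effect) matched 1:1 with expectation left out of, or put into, the propensity model. The caliper was assumed to be 0.2 SD of the logit, not the SAP's 0.001.

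| Effect on choice (log odds per SD) / on outcome (SD per SD) | Omitted: bias, rejection, pairs | Included: bias, rejection, pairs |
|---|---|---|
| 0 / 0.3 | −0.001, 3.8%, 190 | 0.000, 6.2%, 190 |
| 0.3 / 0.3 | 0.090, 13.5%, 193 | 0.004, 5.0%, 191 |
| 0.5 / 0.3 | 0.137, 26.8%, 196 | 0.001, 4.2%, 191 |
| 0.5 / 0.5 | 0.237, 67.8%, 197 | −0.010, 3.5%, 191 |

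Monte Carlo SE at 5% is √(0.05 × 0.95/400) = 1.1 percentage points, so 3.5% to 6.2% is compatible with 5%. The simulation treats expectation as fixed before the choice of drug. It does not test reimbursement status, nor the pair loss at a caliper of 0.001.

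**The case against.** The strongest objection is timing. Protocol 9.2 requires the treatment decision to precede enrolment, and Protocol 9.2.3 allows no data collection before consent. PACT-Q1 is therefore answered once the drug is known, and may partly reflect that drug and what the patient was told about it. Requiring completion before the first dose does not cure this, because assignment happens at the decision. A reader might infer that PACT-Q1 belongs in the primary propensity model. The documents do not support that, since it could mean adjusting for a consequence of the choice. This part of the objection stands, and it moves PACT-Q1 to an adjusted analysis shown beside the main one.

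Second, the Pradaxa reimbursement criteria in Protocol section 7 overlap heavily with variables already in the model (age, stroke history, renal function), and reimbursement status may be tied to the drug received. Forcing it in could damage overlap, above all at the 0.001 caliper. This stands as a condition on the fix.

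Third, balance checking is partly planned. Protocol 9.7.1 and SAP 8.7 compare baseline characteristics after matching, Protocol 9.7.1 adds standardized differences, and PACT-Q1 is to be described by treatment. It would be too strong to say that an imbalance could not be seen. But SAP 9.3 leaves reimbursement status out of its summary sentence, Protocol 9.3.4 lists neither variable among baseline characteristics, and no step follows if an imbalance appears.

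Fourth, SAP 8.4 introduces its list with the word including, Protocol 9.3.3 allows further covariate analyses, and the protocol abstract calls the study essentially descriptive. Additions are thus not barred. None is pre-specified, however, and SAP 11.6 still concludes from a significance test.

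**Conclusion.** The point holds as a risk of confounding that the plan names but does not address. Reimbursement status and the nearest baseline measure of perception are both collected in Cohort B, and neither is used in the primary comparison.

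A reader might go further and say that the comparison is confounded. The documents cannot show that: they give no imbalance and no correlation, and if expectation does not affect choice the bias is about zero. Nor is perception in Protocol section 7 literally PACT-Q1, which measures expectations. A reader might also count education level among the named drivers. Section 7 speaks of educational measures about medications, not of schooling, so that variable is optional.

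On assumed r and d of 0.1 to 0.5, the bias is 0.01 to 0.25 SD and the false-positive rate 5.1% to 70.5%. The upper figures need both inputs at the top of their range and all 200 VKA patients matched and assessed. With fewer pairs the bias is unchanged and the false-positive rate is lower. The change is worth making because it needs no new data, and neither the optional wording nor the balance check takes its place.

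**What to change.** - **SAP 8.4:** add reimbursement status to the Cohort B propensity model if overlap permits, judged from a cross-tabulation with drug before any PACT-Q2 data are examined. Otherwise adjust for it in the outcome model.
- **SAP 8.7 and 9.3:** report post-match standardized differences for reimbursement status and PACT-Q1.
- **SAP 11.3:** pre-specify a regression of PACT-Q2 on treatment in the matched sample, at Visit 2 and at Visit 3, adjusted for PACT-Q1 and reimbursement status and allowing for the pairing. Report it beside the unadjusted paired result, which stays as Protocol 9.7.1 has it.
- **Interpretation:** state that PACT-Q1 is completed after the treatment decision and may partly reflect the chosen drug, so the two results should be read together.

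The cost is SAP wording, one extra analysis and possibly fewer matched pairs at the 0.001 caliper; how many fewer cannot be told from the documents. SAP 8.5 rules out imputation, so the adjusted analysis will also lose patients without a PACT-Q1 score. Education level may be added but is not needed for this point.

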## 8.5 Missing Data

No imputation method will be performed to estimate the missing values for efficacy and safety variables.

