### Full Analysis Set (FAS)

All eligible patients.

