#### 10.2 Primary Endpoint(s)

##### Cohort A (patients switched from VKA to Pradaxa®)

- Mean change in the PACT-Q2 scores at the second assessment (30-45 days) and the last assessment (150-210 days) compared to baseline assessment. The changes will be calculated as (PACT-Q2 scores at Visit 2 minus PACT-Q2 scores at visit 1, PACT-Q2 scores at Last Visit minus PACT-Q2 scores at visit 1).

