##### Cohort B (patients newly initiated Pradaxa® or VKA)

- Mean difference in the PACT-Q2 scores at the second (30-45 days) and the last assessment (150-210 days) compared between 2 treatment groups. The difference will be calculated as (PACT-Q2 scores of *Pradaxa®* minus PACT-Q2 scores of VKA at Visit 2, PACT-Q2 scores of *Pradaxa®* minus PACT-Q2 scores of VKA at Last Visit).

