### 11.2 Test of Assumptions

The primary hypothesis will be tested by paired t-test. The assumption of normality will be tested by using the Shapiro-Wilk test. Wilcoxon signed rank test will be used if the assumption of normally distributed is violated.

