### 11.3 Primary Endpoint Analysis

Mean values and mean change from baseline of PACT-Q2 scores will be presented as descriptive statistics including Number, Mean $\pm$ SD, Median, Range, inter-quartile range (IQR), 25th percentile, 75th percentile and 95% C.I. The changes under Cohort A will be calculated as (PACT-Q2 scores at Visit 2 minus PACT-Q2 scores at visit 1, PACT-Q2 scores at Last Visit minus PACT-Q2 scores at visit 1). The difference under cohort B will be calculated as (PACT-Q2 scores of Pradaxa® minus PACT-Q2 scores of VKA at Visit 2, PACT-Q2 scores of Pradaxa® minus PACT-Q2 scores of VKA at Last Visit). Shapiro-Wilk test will be conducted for testing the normality. If the null hypothesis of normally distributed of Shapiro-Wilk test is not reject, two-sided paired t-test will be performed and obtain the p-value. Significant level of the test will be set as 0.05. Once significant result of Shapiro-Wilk test is lower than 0.05, Wilcoxon signed rank test will be used instead.

For cohort B, the patients newly initiated Pradaxa® or VKA will be matched with a ratio of 1:1 based on the propensity score with caliper matching. After the propensity score each patient is generated, both Pradaxa® group and VKA group should be randomly sorted and then the first VKA unit is selected to find its closest

Pradaxa® match in terms of the propensity score. The random seed will be set as 20190218. The caliper will be set as 0.001.

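### The primary PACT-Q2 tests use only patients or pairs with both scores, and a normality pre-test can displace the test of the mean; one prespecified mixed model on all observed scores would suit the stated endpoints better

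*SAP*

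**What the plan says.** The SAP defines the primary endpoints as means. For Cohort A (SAP 10.2) it is "Mean change in the PACT-Q2 scores at the second assessment (30-45 days) and the last assessment (150-210 days) compared to baseline assessment"; for Cohort B it is "Mean difference in the PACT-Q2 scores at the second (30-45 days) and the last assessment (150-210 days) compared between 2 treatment groups".

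SAP 9 places efficacy on the Full Analysis Set, which SAP 8.3 defines as "All eligible patients", with no requirement that a score be present. SAP 8.5 adds: "No imputation method will be performed to estimate the missing values for efficacy and safety variables".

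The tests are paired. Protocol 9.7.1 says for Cohort B: "PACT-Q2 score will be compared between matched Pradaxa® initiators and VKA initiators using paired t-test or Wilcoxon signed-rank test". SAP 11.3 makes the choice of test depend on a normality test: "Once significant result of Shapiro-Wilk test is lower than 0.05, Wilcoxon signed rank test will be used instead". SAP 11.4 repeats the rule for the secondary comparison. SAP 11.6 draws the conclusion from p < 0.05.

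For matching, SAP 11.3 sorts both groups at random and then "the first VKA unit is selected to find its closest" Pradaxa counterpart. It does not say whether patients without PACT-Q2 scores are removed before or after this step.

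Protocol 9.2.3 makes follow-up depend on routine attendance, with no study-only visits. Protocol 9.7.4 leaves imputation open, to be described in the SAP, and gives 10% as an example of a loss large enough to investigate.

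**The concern.** A paired test without imputation cannot use a patient who lacks one of the two scores, so the set tested is smaller than the FAS once scores are missing. In Cohort B the cost depends on the unstated order. If everyone is matched first, which is the natural reading of the FAS definition and protocol 9.7.1, one missing score removes two patients from the test. If patients without scores are removed first, no pair is broken.

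Missing scores are foreseeable because questionnaires are collected only at routine face-to-face visits. If absence is related to satisfaction, complete-case estimates can be biased. Neither document plans a repeated-measures model or a sensitivity analysis for missing scores; protocol 9.7.4 describes lost patients but does not change the estimate.

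The second issue has lower priority. The endpoint is a mean, but the test that decides the conclusion may be a signed-rank test. With skewed changes that test does not address mean change = 0, so the p-value and the reported mean with its 95% CI can answer different questions.

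**Working it through.** **Inputs from the documents.** Cohort A n = 300; Cohort B 500 Pradaxa and 200 VKA, matched 1:1, so at most 200 pairs (fewer if the 0.001 caliper leaves patients unmatched); two-sided alpha 0.05. The documents give no SD, correlation, effect size or expected loss, so there is no figure of the plan to reproduce.

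**Assumptions.** Loss 5%, 10% or 20%, with 10% central only because protocol 9.7.4 names it; loss at Visit 3 only; SD 15 for the Cohort A change and for each Cohort B score; visit-to-visit correlation 0.6 and within-pair correlation 0.1 in Cohort B.

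**1. Cohort B pairs and precision under random loss d per arm.** Complete pairs are 200(1-d)² if matched first, and up to 200(1-d) if matched after exclusions. The variance of the paired difference is 2 × 15² × (1 - 0.1) / pairs = 405 / pairs. The model variance is the generalised least squares variance using every observed score from the 200 pairs.

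| Loss per arm | Pairs, matched first | Pairs, after exclusion | Variance, first | Variance, after | Model | Ratios to model |
|---|---|---|---|---|---|---|
| 5% | 180 | 190 | 2.24 | 2.13 | 2.10 | 1.07 / 1.02 |
| 10% | 162 | 180 | 2.50 | 2.25 | 2.18 | 1.14 / 1.03 |
| 20% | 128 | 160 | 3.16 | 2.53 | 2.38 | 1.33 / 1.06 |

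**2. Cohort A bias at 10% loss.** The odds of loss double for each SD that the driver of loss is lower. Score correlations are 0.5 (Visits 1 and 2), 0.5 (Visits 1 and 3) and 0.6 (Visits 2 and 3), which give a correlation of 0.6 between the two changes and a score SD of 15. Among patients still observed, the mean of the driver is shifted by about 0.98/15 = 0.065 SD. For normal scores, complete-case bias = 0.065 × 15 × r = 0.98r, where r is the correlation of the driver with the Visit 3 change. Simulation agrees to within 0.01. The model is an unstructured likelihood model on all three visits.

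| Loss follows a low | r | Complete-case bias | Model bias |
|---|---|---|---|
| Baseline score | -0.5 | -0.5 | about 0 |
| Visit 2 score | 0.1 | 0.1 | about 0 |
| Visit 2 change | 0.6 | 0.6 | about 0 |
| Visit 3 score (unseen) | 0.5 | 0.48 | 0.58 |
| Visit 3 change (unseen) | 1.0 | 1.0 | 0.6 |

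Other score correlations move the Visit 2 score row between about 0 (all correlations equal) and 0.2. All signs reverse if the odds of loss rise with the driver instead. The SE is 15/√(300 × 0.9) = 0.91, so a bias of 0.6 is about 0.65 SE and cuts the coverage of a 95% CI to about 90%.

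The model does worse in the fourth row for a simple reason. The Visit 3 variance left unexplained by Visits 1 and 2 is 0.587 of the total, so its bias is 0.98 × 0.587 = 0.58. The complete-case change subtracts a baseline that is selected in the same direction, which leaves 0.98 × 0.5 = 0.49.

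**3. Cohort B bias.** Loss that acts equally in both arms roughly cancels. With 10% Pradaxa and 20% VKA loss, the bias is 0.6 points in size if loss follows the Visit 2 score and 0.9 if it follows the unseen Visit 3 score (model 0.0 and 0.6). The SE is √(450/144) = 1.77, with 200 × 0.9 × 0.8 = 144 pairs and pair correlation 0.

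**4. The normality switch, n = 300, true mean change exactly 0 (centred gamma, 4,000 replicates).**

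| Skewness of changes | Normality rejected | Switched procedure rejects | t-test rejects |
|---|---|---|---|
| 0.25 | 34% | 6.6% | 5.2% |
| 0.5 | 89% | 10.2% | 5.4% |
| 1.0 | 100% | 31.2% | 4.7% |

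Repeated simulations gave 9.5% to 12% at skewness 0.5 and 28% to 31% at skewness 1. With exchangeable skewed baseline and follow-up scores the rate is 5.0%, although normality is rejected in 99.7% of samples. With two similarly shaped skewed arms and 200 pairs it is 5.2%.

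**The case against.** The study calls itself essentially descriptive, protocol 9.7.1 names the paired tests, and protocol 9.7.4 lets the SAP decide on imputation. SAP 8.5 is therefore a permitted choice and not an error; a likelihood model imputes nothing either. That stands, and the point concerns the analysis method. The 10% is an example trigger and not a forecast, and every SD, correlation and loss mechanism above is assumed. That also stands.

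A reader might infer that complete-case analysis overstates the benefit of switching because dissatisfied patients leave. The documents give no direction of loss, and the second table shows an understated change when patients dissatisfied at baseline leave and almost no bias when loss follows the Visit 2 score. A reader might also infer that a mixed model always removes at least part of the bias. It does not: if loss depends on the unseen Visit 3 score, it can be slightly worse than complete cases.

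On the switch, the high rejection rates need skewed changes whose mean is exactly zero, and the mean and 95% CI are reported whichever test is used. So the mean estimate is kept; what can change is the p-value from which SAP 11.6 concludes. A large true change would stay significant under either test.

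A mixed model could be called a preference. But it fits the mean endpoints, uses data already collected, and is nearly unbiased in every case examined where loss depends on an observed score.

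**Conclusion.** The point holds as a recommended improvement, with medium confidence. That the primary tests use only complete patients or pairs follows from SAP 8.5 with the paired tests; that the normality switch can replace the test of the mean is explicit in SAP 11.2 to 11.4.

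The loss of precision in Cohort B is a variance ratio of 1.14 at 10% loss if matched first, and only 1.03 if matched after exclusions. In Cohort A the possible bias from loss that depends on an observed score runs from about -0.5 to +0.6 points against an SE of 0.91, with neither sign nor size settled by the documents. Under completely random loss there is no bias and the gain is precision alone. The switch matters from a skewness of about 0.5 and not for symmetric changes.

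**What to change.** - **SAP 11.2 to 11.4:** drop the Shapiro-Wilk switch. Make the primary analysis one prespecified linear mixed model on all observed scores, fitted for each PACT-Q2 score analysed, since protocol 9.3.5 describes three dimensions. Cohort A: visit effect, unstructured within-patient covariance, baseline as a response. Cohort B matched set: treatment by visit, allowing for matched pair and repeated measures.
- **Reporting:** take the estimate, 95% CI and p-value from that model. Keep the paired t-test and Wilcoxon test as sensitivity analyses, and add a simple delta-shift analysis for loss that is not at random.
- **SAP 11.3:** state that matching uses all eligible Cohort B patients, whether or not PACT-Q2 scores are present.
- **SAP 12:** declare the departure from protocol 9.7.1, with a protocol amendment if required. SAP 8.5 can stay and cross-refer to the comparison of lost and completed patients in protocol 9.7.4.

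The cost is SAP text and standard software, with no new data. The downside is the missing-at-random assumption: if loss depends on the unseen Visit 3 score, the model's bias is about 0.58 points against 0.48 for complete cases at 10% loss, which is why the delta-shift analysis is needed. Cohort B has no baseline PACT-Q2, so a patient missing both follow-up scores still contributes nothing.
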